6.3.3 Investigational Period (Day 1 to Day 5)

On Day 1, subjects will be randomized to one of two product use sequences of the P4M3 variants in order to cross-over the use of P4M3-1.7% and P4M3-1.7%LA:

Sequence 1:

P4M3-1.7%; P4M3-1.7%LA; P4M3-3%LA; and P4M3-4%LA

Sequence 2:

P4M3-1.7%LA; P4M3-1.7%; P4M3-3%LA; and P4M3-4%LA

On Days 1 to 4, subjects will be provided and instructed to use a new, ready-to-use product (full cartridge) of the assigned P4M3 variant for fixed puffing regimen with HPT recording in the morning and another new one for the *ad libitum* use for 60 minutes with HPT recording in the afternoon, according to one of two randomly assigned sequences. The concentration of P4M3 e-liquid will be the same on a given day for fixed puffing and *ad libitum* use on Days 1 to 4. T0 for 60 minutes *ad libitum* use should be at least 10 hours after T0 for fixed puffing to allow adequate characterization of nicotine plasma AUCs. There will be a washout of at least 10 hours following each *ad libitum* product use with respect to the subsequent fixed puffing regimen in the next morning to allow adequate background correction of the fixed puffing regimen-related nicotine plasma concentrations.

Following product use on each day, the used e-liquid cartridges will be collected for assessment of e-liquid use. E-liquid cartridges will be weighed prior and post product use.

Except for the test products, subjects will not be allowed to use any nicotine-containing products through Discharge or early termination.

Subjects will be continuously supervised during P4M3 usage.

Data and information contained in this document are considered to constitute trade secrets and confidential commercial information, and the legal protections provided to such trade secrets and confidential information are hereby claimed under the applicable provisions of US law. No part of this document may be publicly disclosed without the written consent of PMI.

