6.7.2 Dietary and Activity Restrictions

A standard diet will be designed by a dietician for the whole confinement period. For each meal, the caloric and fat content should be controlled in order to avoid a "high-fat" diet. A "high-fat" diet is a diet which contains "approximately 50 percent of total caloric content of the meal [from fat] and is high in calories (approximately 800 to 1000 calories) (FDA, 2002).

Subjects should refrain from ingesting foods or beverages containing grapefruit or seville-type (sour) oranges and marmalade, apple, orange, pineapple, vegetables from the mustard green family (e.g., kale, broccoli, watercress, collard greens, kohlrabi, Brussels sprouts, mustard), and charbroiled meats from 7 days prior to Day -2 and throughout the study.

Subjects are not allowed to bring their own food or beverages to the investigational site. Water, light snacks, fruits, and raw vegetables can be distributed to the subjects without restrictions at any time during confinement as long as they comply with the dietician's standard diet. Consumption of food or beverage (including water) will not be allowed during each product use on Day -1 to Day 4. The same menu and meal schedule will be administered uniformly for all subjects. Fasting state has to be observed for at least 12 hours prior to blood drawings for the safety laboratory on Day -2, Day 2, and Day 5.

Subjects should refrain from strenuous and/or unaccustomed exercise throughout the entire course of the study.

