7.5.1 Clinical Chemistry, Hematology, and Urine Analysis for Safety Panel

Hematology, clinical chemistry, and urine analysis for the safety panel will be measured at the Screening Visit, at Admission (Day -2), at Day 2 and at Discharge (Day 5) or early termination. Tests will be conducted at a local laboratory or at the investigational site. Except for the Screening visit, blood will be taken after no less than 12 hours of fasting (see [Section 6.7.2](#)). The urine test will be performed semi-quantitatively as urine dip-stick test at the site. Parameters to be measured are listed in [Table 2](#).

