8.4 Reporting of Other Events Critical to Safety Evaluations

8.4.1 Abnormal Results of Laboratory Tests

Any clinical safety laboratory test result that is outside of the normal reference range will be reviewed by the Investigator and assessed for clinical significance according to its severity. The severity of abnormal laboratory test result must be assessed using CTCAE version 4.0 grading scale, available in [Appendix 3](#). Whenever that grading scheme is not available for the laboratory result of concern, the Investigator should assess the severity and the clinical significance of that result using his/her medical judgment.

Abnormal laboratory test results detected at the Screening Visit whose CTCAE grades are 2 or higher or still are CTCAE grade 1 and deemed clinically significant are usually concomitant disease or a manifestation of one and must be recorded accordingly. However, in some instances, they may be assessed as AEs (and therefore must be handled according to the directions from [Section 8.2](#) or as manifestations of already reported AEs). This decision will require a careful assessment of the abnormal result within the clinical context on a case-by-case basis and will depend on the Investigator's medical judgment.

Abnormal laboratory test results detected after the Screening Visit whose CTCAE grades are 2 or higher or still are CTCAE grade 1 and deemed clinically significant must be either recorded as AEs (and handled according to the directions in [Section 8.2](#)) or linked to a concomitant disease or still to an already reported AE.

The principles for assessing and reporting abnormal laboratory test results, emerging after the Screening Visit, using the CTCAE version 4.0 grading scale, are set up in [Table 4](#):

Table 4. Principles for Assessing and Reporting Abnormal Laboratory Test Results

Grading	Clinically significant?	Is it a worsening from previous results in study? [§]	Report?
Grade 1	No	Not applicable	No
Grade 1	Yes	No	No*
Grade 1	Yes	Yes	Yes, as AE or linked to an already reported AE
Grade 2 or higher	No/Yes	No	No*
Grade 2 or higher	No/Yes	Yes	Yes, as AE or linked to an already reported AE

* In this situation, this abnormal lab test result is either a manifestation of a concomitant disease or of an already reported AE.

[§] Grade increase in this context means the value is higher than the one from the screening visit.

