9 STUDY ACTIVITIES

A detailed schedule of assessments can be found in [Appendix 1](#). The investigational site may adjust the start times of scheduled events as long as the necessary relative timing of the previous and subsequent events are maintained. Measurements not conducted at the exact time point, but conducted within the given time window (if applicable) do not constitute a protocol deviation but an accepted variability for the scheduled time point.

In general, if no start time for the procedure is provided, then the procedure can be performed at any time during the day.

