**Table 8. Event Schedule – Fixed Puffing and *Ad Libitum* Product Use with P4M3 Variants (Days 1 to 4)**

Blood sample	Procedures	Additional information
	Optional morning snack	
	Randomization (Day 1 only)	Sequence 1: P4M3-1.7%; P4M3-1.7%LA; P4M3-3%LA; and P4M3-4%LA Sequence 2: P4M3-1.7%LA; P4M3-1.7%; P4M3-3%LA; and P4M3-4%LA
√	Nicotine baseline plasma sampling prior P4M3 variants use	One blood sample will be taken prior to the start of product use (T0): 15 minutes ± 5 minutes (T-1).
√	Clinical laboratory parameters (hematology, urine analysis, clinical chemistry) (Day 2 only)	Fasting state
	Vital signs prior product use	At least 5 minutes in supine position prior to measurement
	VAS for craving prior product use (x1 T0)	
	Washout	Minimum of 10 hours
	Fixed puffing P4M3 variants with HPT	Fixed puffing regimen comprising of 12 puffs in total at a rate of one puff every 30 seconds (± 5 seconds)
√	Plasma samples for nicotine	Post T0, blood will be drawn at the following time points: T1 after 2 minutes ± 30 seconds, T2 after 4 minutes ± 1 minute, T3 after 7 minutes ± 1 minute, T4 after 10 minutes ± 1 minute, T5 after 15 minutes ± 2 minutes, T6 after 30 minutes ± 2 minutes, T7 after 1 hour ± 5 minutes, T8 after 2 hours ± 5 minutes, T9 after 4 hours ± 5 minutes.

VAS Craving assessment	Post T0, VAS assessments will be assessed at the following time points 4 minutes (± 2 minutes) 10 minutes (± 2 minutes) 15 minutes (± 2 minutes) 30 minutes (± 5 minutes) 1 hour (± 10 minutes) 2 hours (± 10 minutes) 4 hours (± 10 minutes)
SQ assessment	Within 60 minutes after completion of product use
Assessment of cough (VAS, three Likert scales and one open question)	Completed by the subject on site within 30 minutes of product use
Vital signs	At least 5 minutes in supine position prior to measurement, to be conducted at 60 minutes ± 10 minutes post end of product use
Device events malfunctions/misuse	As reported post product use
Washout	Minimum 10 hours
Lunch	
Vital signs pre-product use	At least 5 minutes in supine position prior to measurement
VAS for craving prior product use (x1 T0)	
√ Nicotine baseline plasma sampling (x1 T0) prior P4M3 variants ad libitum use	One blood sample will be taken prior to P4M3 variants ad libitum use (T0): 15 minutes ± 5 minutes (T-1)
Ad libitum use P4M3 variants with HPT	Ad libitum use for 60 minutes (± 5 minutes) with HPT recording

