9.5 Early Termination Procedures

The following assessments will be conducted after a subject is prematurely discontinued from the study ([Table 10](#)):

Table 10. Event Schedule – Early Termination

Blood sample	Procedures	Additional information
	AE/SAE recording, concomitant medication	
	Assessment of cough (VAS, three Likert scales and one open question)	
√	Clinical laboratory parameters (hematology, urine analysis, clinical chemistry)	
	Urine pregnancy test for female subjects	
	Vital signs	At least 5 minutes in supine position prior to measurement
	ECG	At least 10 minutes in supine position prior to recording
	Spirometry without short-acting bronchodilator	
	Physical examination	
	Time of early termination	

Abbreviations: AE = Adverse event; ECG = Electrocardiogram, SAE = Serious adverse event

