12.6.3 Safety Endpoints

In general, all safety data will be listed and tabulated using the approach described in [Section 12.1.2](#). Safety variables collected during exposure periods will also be reported by product exposure.

AE data will serve as the primary assessment of safety. Other safety variables monitored in this study include: respiratory symptoms (cough assessment VAS and Likert scales); vital signs (systolic and diastolic blood pressure, pulse rate, respiratory rate); spirometry; ECG data; clinical chemistry, hematology, and urine analysis safety panel; physical examination.

Data and information contained in this document are considered to constitute trade secrets and confidential commercial information, and the legal protections provided to such trade secrets and confidential information are hereby claimed under the applicable provisions of US law. No part of this document may be publicly disclosed without the written consent of PMI.

All AEs will be summarized by nicotine concentration (fixed puffing and *ad libitum* use combined) and overall. The number and percentage of subjects with AEs, SAEs, and device events will be tabulated by system organ class and preferred term. Summaries will also be presented for AEs leading to discontinuation, AEs leading to death, AEs by relatedness to product exposure (with and without laboratory related AEs), AEs by severity, and laboratory AEs. Tabulations will be performed for both the number of subjects experiencing an event and the number of events. Due to the laboratory schedule in this study, any lab related AEs will be assigned to P4M3 4% nicotine concentration.

Summary tables showing actual values and change from baseline of clinical findings will be provided for spirometry, ECGs, vital signs, and laboratory parameter. Descriptive statistics will be summarized by fixed puffing/*ad libitum* use and nicotine concentration and change from baseline will be presented for laboratory parameters, ECG, respiratory symptoms, and vital signs. Shift tables will be provided for laboratory and safety ECG data.

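### Section 12.6.3 counts every laboratory AE under P4M3 4%, including those found on panels drawn before any 4% use

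*Protocol*

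**What the plan says.** Section 12.6.3 plans AE summaries by nicotine concentration and overall, with a separate summary of laboratory AEs. For these it sets one attribution rule and gives its reason: "Due to the laboratory schedule in this study, any lab related AEs will be assigned to P4M3 4% nicotine concentration". The rule has no exception for the date of the panel or for subjects who never used the 4% product.

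Section 7.5.1 schedules the safety panel at Screening and then "at Admission (Day -2), at Day 2 and at Discharge (Day 5) or early termination". Section 6.7.2 repeats the dates in its fasting requirement ("prior to blood drawings for the safety laboratory on Day -2, Day 2, and Day 5"), Table 8 lists "Clinical laboratory parameters (hematology, urine analysis, clinical chemistry) (Day 2 only") among the procedures for the product-use days, and Appendix 1 marks the same day. Table 10 in Section 9.5 includes the panel at early termination.

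Section 6.3.3 gives one variant per day on Days 1 to 4. Sequence 2 reads "P4M3-1.7%LA; P4M3-1.7%; P4M3-3%LA; and P4M3-4%LA". Sequence 1 swaps only the first two products.

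**The concern.** The rule would follow from the laboratory schedule only if every panel after the start of P4M3 use came after the 4% use. That is true of Day 5. It is not true of Day 2, nor of an early termination before the Day 4 session.

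This is a concentration-ranging study with AEs as the main safety assessment, so the by-product AE tables are where a reader looks for a trend with nicotine concentration. Under the rule, the 4% column collects every laboratory AE and the other columns collect none. An apparent laboratory signal at the top concentration could be produced by the rule alone, and a real one at a lower concentration would be hidden. The rule also conflicts with Section 12.3, which bases all analyses on the product actually used.

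**Working it through.** **Step 1: what has been used when each panel is drawn.** The panel dates come from Sections 7.5.1 and 9.5, and the product order from Sections 6.3.1 to 6.3.3.

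| Panel | Variants used before it, Sequence 1 | Variants used before it, Sequence 2 | 4%LA used? |
|---|---|---|---|
| Day 2, before that day's use | 1.7% | 1.7%LA | No |
| Day 2, after that day's use | 1.7%, 1.7%LA | 1.7%LA, 1.7% | No |
| Early termination, Days 1 to 3 | at most 1.7%, 1.7%LA, 3%LA | the same three | No |
| Early termination, Day 4 before first puff | 1.7%, 1.7%LA, 3%LA | the same three | No |
| Early termination, Day 4 after use | all four | all four | Yes |
| Day 5 | all four | all four | Yes |

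The product test with P4M3-1.7% (Day -2) and the subject's own e-cigarette (Day -1) come before all of these panels.

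Table 8 lists the Day 2 panel as fasting and ahead of fixed puffing. Section 9 allows that "if no start time for the procedure is provided, then the procedure can be performed at any time during the day". The clock time does not matter here: first 4% use is two days later in both sequences.

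**Step 2: can these panels produce AEs?** Yes. Section 8.4.1 deals with "Abnormal laboratory test results detected after the Screening Visit whose CTCAE grades are 2 or higher", and with Grade 1 results judged clinically significant. They are recorded as AEs or linked to a concomitant disease or an existing AE. Table 4 narrows this to results that worsened, with Screening as the comparison. A new abnormality on Day 2 meets that condition.

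**Step 3: how many panels precede 4% use?** The Synopsis randomizes 16 so that 12 complete, which allows for 4 non-completers (16 − 12). Of these 4, let *j* leave before the Day 2 panel, *k* leave between that panel and the Day 4 use, and the rest leave after 4% use. Assume each has the early-termination panel.

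- Total post-randomization panels: Day 2 (16 − *j*) + Day 5 (12) + early termination (4) = 32 − *j*.
- Panels before any 4% use: (16 − *j*) + *j* + *k* = 16 + *k*.
- Share: (16 + *k*) / (32 − *j*).

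Results:

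- All 16 complete: 16 Day 2 + 16 Day 5 = 32 panels; 16/32 = 50%.
- All four leave after 4% use (*j* = 0, *k* = 0): 16/32 = 50%.
- All four leave before the Day 2 panel (*j* = 4, *k* = 0): 16/28 = 57.1%.
- All four leave between the Day 2 panel and the Day 4 use (*j* = 0, *k* = 4): 20/32 = 62.5%.

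**The case against.** The best defence is that no rule can attribute laboratory AEs cleanly here. With two scheduled panels and four variants, each panel reflects mixed exposure. Assigning by last product does not remove all the zeros: every Day 5 finding in a completer still goes to 4%LA, so 3%LA receives no laboratory AEs from completers. If the Day 2 sample is drawn before use, each 1.7% variant receives Day 2 findings only from the sequence that used it on Day 1. That stands, and the footnote proposed below should say so. It does not justify crediting an event to a product used only afterwards.

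A second defence is that little is at stake. Subjects are healthy and screened for renal and hepatic abnormality. There are 16 of them and no hypothesis test. All safety data are listed, overall summaries and shift tables are planned, and the relatedness tables are shown with and without laboratory AEs. This is fair, and it limits the weight of the point.

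The Synopsis restricts by-product AE tables to events emergent under a P4M3 variant. That keeps Day -2 findings out, but not Day 2 findings: those can emerge after the Day 1 variant and cannot emerge after 4%.

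Finally, Section 12.2 describes its 25% allowance as subjects with at least one incomplete exposure period, which is not the same as non-completion. The figure of four therefore rests on the Synopsis.

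**Conclusion.** The concern holds. Followed as written, the rule gives wrong by-product counts for any laboratory AE first detected on Day 2 or at an early termination before 4% use, and its stated reason is contradicted by the protocol's own schedule. Nothing in the protocol limits it to Day 5 findings.

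One of the two scheduled post-randomization panels precedes 4% use: 50% of panels if all subjects complete, and 50% to 62.5% with four non-completers. The timing of dropout, and an early-termination panel for every leaver, are assumptions. The share of laboratory AEs affected cannot be estimated because no rate is given.

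The damage is confined to the by-product allocation of laboratory AEs. Other AEs, the overall column, tables that leave out laboratory AEs, and the PK endpoints are untouched.

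**What to change.** Replace the sentence in Section 12.6.3 with:

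> Each laboratory AE will be assigned to the last product used before the sample in which the abnormality was first detected, using recorded sample and product-use times. Laboratory AEs first detected before any randomized P4M3 variant is used will be kept out of the variant columns and listed separately (product test or own e-cigarette). Laboratory AEs will also be tabulated by panel (Day 2, Day 5, early termination) and for P4M3 overall.

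Add a footnote that exposure since the previous panel is mixed. For Day 2 it covers the product test, the own e-cigarette and the Day 1 variant, plus the Day 2 variant if the sample followed that use. For Day 5 it covers the variants used on Days 2 to 4. The footnote should also say that 3%LA receives no laboratory AEs from completers under this rule.

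The cost is one sentence, one footnote and one programming rule. Product-use start and stop times are already logged (Section 6.6.1). The protocol does not say that safety-sample clock times are recorded, but the sample date alone separates Day 2 from Day 4. A clock time is needed only when a panel and a product use fall on the same day.

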6.3 Use of Investigational Products

Subjects will never be forced to use the products and will be free to stop using the products at any time during the study. Subjects caught using any nicotine/tobacco product which is different from the assigned IP will be discontinued from the study. During the screening period, subjects will be allowed to use e-cigarettes according to their usual habits except during the procedures of the Screening Visit.

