7.3.9 Other Clinical Assessments

7.3.9.1 Spirometry

Spirometry with and without a short-acting bronchodilator will be done at the Screening Visit to evaluate inclusion/exclusion criteria. A spirometry without a bronchodilator will be performed at the time of discharge on Day 5 or at early termination.

Spirometry will follow the 2005 testing and quality recommendations by the American Thoracic Society/European Respiratory Society Joint Task Force on the standardization of spirometry along with the electronic data submission and documentation processes ([American Thoracic Society \[ATS\], 2005](#)). Spirometry predicted values will be standardized to the National Health and Nutrition Examination Survey III predicted set ([Hu and Cassano \(NHANES III\), 2000](#)).

All personnel performing lung function testing should have the appropriate training and quality control measures should be put into place and be properly documented and filed at the pulmonary function laboratory (including the records of the calibration, if applicable).

Data and information contained in this document are considered to constitute trade secrets and confidential commercial information, and the legal protections provided to such trade secrets and confidential information are hereby claimed under the applicable provisions of US law. No part of this document may be publicly disclosed without the written consent of PMI.

The subject will be submitted to a spirometry with maximum voluntary ventilation measurement.

For spirometry, assessed parameters will include:

- FEV₁
- FEV₁ % Predicted
- FVC
- FEV₁/FVC

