7.3.9.2 Electrocardiogram

An ECG will be recorded at Screening and at Discharge (Day 5) or at early termination. The ECG testing will be performed as per the investigational site standard practice. A standard 12-lead ECG will be recorded after the subject has rested for at least 10 minutes in supine position.

The following parameters will be documented: heart rate, PR interval, QRS interval, QT interval, and QTc interval, corrected by the ECG device according to Bazett's formula and Fridericia's formula. Every ECG has to be assessed as normal, abnormal – clinically not relevant, or abnormal – clinically relevant. A diagnosis has to be provided in the CRF for all ECGs assessed as abnormal – clinically relevant. ECG print-outs will be interpreted by a qualified physician and included in the Source Data File.

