12.1.1 Definitions for Statistical Data Analysis

Unless otherwise stated, for the purposes of statistical analyses, baseline is defined as the last available time point prior to T0 on Day -1.

Nicotine exposure parameters will be derived from plasma nicotine versus time data by NCA using Phoenix WinNonlin, Version 7.0 or higher. C_{max}, AUCs, and related PK parameters, as appropriate, will also be calculated. To minimize the potential bias in the nicotine plasma PK parameters for the fixed puffing regimens, background-concentration correction will be applied to the concentration data and derived PK parameters to adjust for carry-over effects. For nicotine exposure parameters, baseline (C₀) will be defined as the concentration immediately prior to T0 for each session. The baseline correction will be implemented by calculating the nicotine exposure parameters using adjusted concentration values as described below:

The nicotine terminal elimination rate constant λ_z (and $t_{1/2z}$) will be estimated from the Day 5 PK samples (or early termination samples, if available) using a linear regression on the log concentration the pre-T0 time points. The regression analysis should contain data from at least 3 different time points in the terminal phase (including the last quantifiable concentration but excluding the concentration at t_{max}), consistent with the assessment of a straight line on the log-transformed scale. The nicotine plasma background-corrected PK parameters will be derived by performing the NCA on the corrected concentrations.

For the purposes of background-correction of the plasma concentrations post-baseline the following formula will be applied: $cC_t = C_t - C_0 * e^{-\lambda_z t}$. Where, C_t is the corrected concentration at each time point, C_0 is the pre-use baseline concentration, λ_z is the Day 5 (or early termination, if available) terminal elimination rate constant and t is the actual time.

If plasma concentrations cannot be background-corrected in a sufficient number of subjects e.g., in the event that the λ_z (or $t_{1/2z}$) cannot be estimated, modelling approaches may be applied including conventional compartmental analyses. The total (untransformed) PK parameters will be reported and used for statistical analyses instead in case both correction methods are unsuccessful. If warranted, nonlinear mixed-effect modeling using nicotine pooled data across studies may also be used.

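### Section 12.6.3 splits ECG and laboratory summaries by regimen and nicotine concentration, but no scheduled ECG or laboratory value in a completer belongs to a single cell of that split

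*Protocol*

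**What the plan says.** The planned summary is in Protocol Section 12.6.3. Descriptive statistics are to be given by fixed puffing or ad libitum "use and nicotine concentration and change from baseline will be presented for laboratory parameters, ECG, respiratory symptoms, and vital signs". The safety paragraph of the synopsis applies the same split, by regimen and product, to safety measurements other than AEs. Neither place exempts ECG or laboratory values.

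The schedule is set elsewhere:

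- ECG, Section 7.3.9.2: "An ECG will be recorded at Screening and at Discharge (Day 5) or at early termination".
- Safety laboratory, Section 7.5.1: "at the Screening Visit, at Admission (Day -2), at Day 2 and at Discharge (Day 5) or early termination". Table 8 lists "Clinical laboratory parameters (hematology, urine analysis, clinical chemistry) (Day 2 only") as a fasting sample, ahead of that day's fixed puffing.
- Baseline, Section 12.1.1: unless stated otherwise, "baseline is defined as the last available time point prior to T0 on Day -1". This makes Screening the ECG baseline and Day -2 the laboratory baseline.
- Product use, Section 6.3.3: one variant a day on Days 1 to 4, with fixed puffing in the morning and ad libitum use in the afternoon. The two 1.7% variants fall on Days 1 and 2 in either order, 3%LA on Day 3 and 4%LA on Day 4.

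Section 12.6.3 also states that, because of the laboratory schedule, every laboratory-related AE is assigned to the 4% concentration.

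**The concern.** A table by regimen and concentration suggests that each entry describes what happened under that regimen and that concentration. Vital signs and cough are measured around each session and can carry that meaning. ECG and laboratory values are measured at a few visits that follow several sessions, so they cannot.

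The study is meant to help select one or more variants, so product-specific safety tables will be read with that choice in mind. If the ECG and laboratory tables follow the stated split, their cells must either stay empty or hold values that reflect more than the product and regimen named in the row. The laboratory-AE rule shows that the risk is not remote. The authors recognised that the schedule does not allow attribution, and then attributed everything to one concentration.

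**Working it through.** The plan states no figure on this point, so there is none to reproduce. The check counts which P4M3 sessions precede each scheduled record, in both sequences.

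**Cells planned.** 2 regimens × 3 nicotine concentrations (1.7%, 3%, 4%) = 6. By variant, 2 regimens × 4 variants = 8.

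**Rule for filling a cell.** A post-use value belongs to a cell only if the Day 1 to 4 sessions before it come from one regimen and one concentration.

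**Count.** P4M3 sessions before a record = 2 regimens × number of product days completed.

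| Record | Sessions before it | Variants | Concentrations | Regimens | Cells validly filled |
|---|---|---|---|---|---|
| Laboratory, Day 2 (before use) | 2 × 1 = 2 | 1 | 1.7% | both | 0 of 6 |
| Laboratory, Day 5 | 2 × 4 = 8 | 4 | 1.7%, 3%, 4% | both | 0 of 6 |
| ECG, Day 5 | 2 × 4 = 8 | 4 | 1.7%, 3%, 4% | both | 0 of 6 |

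The result is the same for Sequence 1 and Sequence 2, which differ only in which 1.7% variant comes first. The Day 2 draw can be tied to the 1.7% concentration, and to the variant used on Day 1, but not to a regimen. Taking the Day 5 laboratory value against Day 2 instead of baseline does not help: 2 × 3 = 6 sessions lie between them, over three variants and all three concentrations. The 3% and 4% concentrations have no ECG or laboratory value of their own.

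Change from baseline covers still more than these sessions. It also spans the Day -2 product test with P4M3-1.7% and the own e-cigarette use on Day -1.

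**Contrast.** Section 7.3.8 places vital signs before and about 60 minutes after each use, and Section 7.7.4 places the cough assessment within 30 minutes after each use. All 8 P4M3 sessions have their own values, so the split works for these two.

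**Laboratory-AE rule.** The first 3% use is on Day 3 and the first 4% use on Day 4. The Day 2 draw precedes both. An abnormality found then would be assigned to a product the subject has not yet used.

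**Early termination.** A subject who stops early has an ECG and laboratory panel after fewer variants. These would fit a single cell only if the subject stopped on Day 1 between the morning and afternoon sessions.

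**The case against.** The strongest reply is that the sentence has two separate clauses: one sets the split, and the other lists variables with change from baseline. On that reading the list need not carry the split. Two other sentences in Section 12.6.3 help this reading. One limits reporting by product exposure to variables collected during exposure periods. The other announces change-from-baseline tables for spirometry, ECG, vital signs and laboratory values with no split at all. This stands to the extent that the text is partly ambiguous. It does not clear the plan, because the synopsis applies the split to other safety measurements generally.

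A second reply is that table layout belongs to the SAP. Here, however, the protocol states a rule that its own schedule cannot meet, so this is not merely detail left open.

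A third reply is that little depends on these tables. That stands: the protocol tests no hypotheses, AEs are the primary safety assessment, and all safety data are listed.

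Some stronger readings are tempting, but the documents do not support them:

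- A reader might infer that the plan commits to labelling a Day 5 ECG as the effect of one product. Nothing says so; empty cells are equally possible. The only explicit misattribution is the laboratory-AE rule.
- A reader might infer a false fall in FEV1, because "Spirometry with and without a short-acting bronchodilator will be done at the Screening Visit" while Day 5 has only the test without. This needs a very literal reading of the baseline rule, since both Screening tests can count as one time point. The documents give no size for the bronchodilator response.
- A reader might infer that abstinence by Day 5 distorts heart-rate change. Usual e-cigarette use is allowed up to the Screening procedures, but the interval before the Screening ECG is not stated and Table 9 gives no clock time for the Day 5 ECG. Nor is nicotine shown to be gone: Section 4.2 gives a terminal half-life of 17 h, and 14 / 17 is about 0.8 of one half-life at the first Day 5 sample.

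**Conclusion.** The concern holds for ECG and laboratory values. As written, Section 12.6.3 and the synopsis plan a split that fills 0 of 6 cells by concentration, or 0 of 8 by variant, in subjects who complete the study. The laboratory-AE rule conflicts with the Day 2 draw in the same way.

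The conclusion rests on the visit schedule, on the fixed order of 3% and 4% in both sequences, and on Table 8 listing the Day 2 sample before that day's use. It needs no assumption about effect size or variability. It affects only secondary, descriptive safety tables; the pharmacokinetic and pharmacodynamic analyses are untouched. The text should be corrected, but the error does not threaten the study's primary objective.

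**What to change.** In Section 12.6.3 and the synopsis:

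- Summarise ECG and spirometry by visit (Screening, Day 5 or early termination) over all products, and physical examination in the same way at its own visits (Section 7.3.6 adds Day -2).
- Summarise laboratory values by visit (Day -2, Day 2, Day 5 or early termination), with Day 2 shown by the variant used on Day 1.
- Keep the regimen-by-variant split for vital signs and cough.
- Reconcile the laboratory-AE attribution rule with the Day 2 draw, so that a Day 2 finding is not assigned to a concentration not yet used.

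As a minor clarification only, name the Screening test without bronchodilator as the spirometry baseline, to match the Day 5 test.

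The cost is protocol and SAP wording and table shells. No procedure, visit or sample is added.
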